6.5.3 Prohibited Medicines

Prohibited medications during the screening period are as defined in the prior/concomitant therapy exclusion criteria in Section 5.2.

Concomitant administration of M4076 with irinotecan, oral direct thrombin inhibitors, digoxin, and proton pump inhibitors is prohibited.

Concomitant administration of M4076 with clinical substrates of CYP3A4 with narrow therapeutic index is prohibited.

Examples of strong inhibitors of CYP3A4 and P-gp inhibitors or strong inducers of CYP3A4 are provided in [Table 9](#). In order to be enrolled, participants must stop before study intervention administration:

- Strong inhibitors of CYP3A4 or P-gp, stop at least 1 week before study intervention administration.
- Strong inducers of CYP3A4, stop at least 2 weeks before study intervention administration.
- Clinical substrates of CYP3A4 with narrow therapeutic index, stop at least 1 week before study intervention until safety follow-up visit.

Table 9 Clinical Examples of Strong CYP3A and P-gp Inhibitors and CYP3A Inducers and sensitive CYP3A4 substrates with narrow therapeutic index

Transporter	Strong Inhibitor	
P-gp	amiodarone, carvedilol, clarithromycin, dronedarone, itraconazole, lapatinib, lopinavir and ritonavir, propafenone, quinidine, ranolazine, ritonavir, saquinavir and ritonavir, telaprevir, tipranavir and ritonavir, verapamil.	
Enzyme	Strong Inhibitors	Strong Inducers
CYP3A	boceprevir, cobicistat, danoprevir and ritonavir, elvitegravir and ritonavir, grapefruit juice, indinavir and ritonavir, itraconazole, ketoconazole, lopinavir and ritonavir, paritaprevir and ritonavir and (ombitasvir and/or dasabuvir), posaconazole, ritonavir, saquinavir and ritonavir, telaprevir, tipranavir and ritonavir, telithromycin, troleandomycin, voriconazole.	apalutamide, carbamazepine, enzalutamide, mitotane, phenytoin, rifampin, St. John's wort (Hypericum perforatum).
Enzyme	Clinical substrates of CYP3A4 with narrow therapeutic index	-
CYP3A	Astemizole, Cyclosporine, Everolimus, Pimozide, sirolimus, tacrolimus	-

Source: [#Table3-2](https://www.fda.gov/drugs/drug-interactions-labeling/drug-development-and-drug-interactions-table-substrates-inhibitors-and-inducers)

CYP3A = cytochrome P450; P-gp = P-glycoprotein.

Note: Most P-gp inhibitors also inhibit CYP3A.

If the administration of a nonpermitted concomitant drug becomes necessary during the study intervention period, e.g., due to AEs, study intervention must be interrupted, and permanent discontinuation should be discussed with medical monitor.

6.5.4 Other Interventions

Radiation therapy is not allowed on this study except for palliative treatment of lesions that are present at baseline and cause symptoms that cannot be adequately controlled by other means e.g. analgesics. If radiation therapy is required, the study intervention should be withheld for at least 4 half-lives before the administration of radiation and may be resumed once toxicities are Grade ≤ 1 (refer to the M4076 IB for more details). In addition, the Investigator should ensure that tumor assessments are recently obtained and reported as per RECIST 1.1 ([Appendix 9](#)), before initiation of radiation therapy.

6.6 Dose Selection and Modification

The recommendation in Part 1A to proceed to the next DL (including what DL), or to decrease the dose in the next cohort or to expand the current DL to include additional participants will be made by the SMC based on safety, tolerability, and preliminary PK and, if appropriate, Pd data. The SMC receives outputs of a Bayesian dose-toxicity model with estimated DLT probabilities for potential next DLs to support the decision making of the SMC. The Bayesian model ([Appendix 12](#)) will be based on prior information, observed number of evaluable participants and number of participants with DLT. Further details on the Bayesian model are provided in Section [9.4.2](#). Further details on the SMC are provided in Section [6.6.1](#).

Participants are eligible for the Bayesian dose-toxicity model for DLT probability, if they fulfill the criteria of the DLT analysis set, defined in Section [9.3](#).

Detailed justification of the starting dose for M4076 is provided in Section [4.2](#). Details of the dose escalation schema in Section [1.2](#).

6.6.1 Safety Monitoring Committee

During the dose-escalation part (Part 1A) of the study, the SMC will evaluate the safety (including DLTs), tolerability, and available PK, to include at least predefined PK of the previous cohort, and available Pd data. The SMC will decide on dose escalation, de-escalation, additional enrolment on same DL, MTD, or suspension of enrolment. In cases where enrollment of the last participant in a dosing cohort is significantly delayed, the SMC may decide (based on available data) upon enrolment and dose for the next dosing cohort before all participants in a cohort have completed the DLT period. For this participant, the SMC will consider all available data and any subsequent emerging data at a subsequent meeting. An ad-hoc meeting will be convened if this participant experiences a DLT.

The SMC can recommend modifying the schedule of administration. SMC will review PK to determine if adjustment of schedule (to predefined alternative schedules as defined in [Appendix 7](#)) is appropriate during the dose escalation based on the collected data. The usual cohort size is 3 participants, but the SMC can decide to change the size of cohorts. Based on the observed toxicity profile and available PK and Pd, DL(s) that are different to, or higher or lower than the prespecified doses may be tested. The SMC may also recommend changing the dosing regimen.

During the Part 1B of the study, the SMC will monitor the safety and may recommend by consensus on continuation, expansion, and modifications of the study. The SMC may modify the frequency of meetings as deemed appropriate during the study.

The specific working procedures will be described in an SMC Charter, which will be established before first informed consent signed.

6.6.2 Dose-limiting Toxicities – Definition and Criteria

A DLT is defined as any of the following AEs according to the National Cancer Institute Common Terminology Criteria for Adverse Events (NCI-CTCAE) Version 5.0 assessed by the Investigator and/or the Sponsor at any dose, judged not to be related to the underlying disease or any previous or concomitant medication or concurrent condition, occurring during the DLT observation period, which for Part 1A starts on the first day of study intervention (Day 1) and has a duration of 21 days.

Study accrual will be halted, pending discussions with the SMC or the study Sponsor, if there is an occurrence of a Grade 5 toxicity by the NCI-CTCAE Version 5.0 attributable to the treatment regimen or if more than 1 DLT is seen in DL 1 in Part 1A.

The treatment of toxicities with transfusions or growth factors (e.g., granulocyte-colony stimulating factor, erythropoietin) is not permitted during the DLT period and if it occurs will be considered a DLT.

AEs judged as DLT will include:

- Any Grade ≥ 3 non-hematologic AE with exception of:
 - Single laboratory values out of normal range that have no clinical correlate and resolve to Grade ≤ 1 or to baseline within 7 days with adequate medical management or asymptomatic Grade 3 lipase or amylase elevation (> 5 ULN) not associated with clinical manifestation of pancreatitis.
 - Infusion-related reaction resolving within 6 hours from the end of infusion and controlled with medical management (for iv compounds only)
 - Diarrhea persisting < 72 hours after initiation of medical management
 - Nausea and vomiting of ≤ 72 h duration with adequate and optimal therapy
 - Transient (≤ 72 h) fatigue, local reactions, flu-like symptoms, fever, headache, hypertension that resolves to Grade ≤ 1 with adequate treatment
 - Grade 3 non-recurrent skin toxicity that resolves to Grade ≤ 1 in less than 7 days after initiation of medical management
 - Tumor flare phenomenon defined as local pain, irritation, or rash localized at sites of known or suspected tumor that resolve to Grade ≤ 2 within 6 days
 - Any death clearly due to the underlying disease or extraneous causes

- Grade ≥ 3 neutropenia with clinical signs/symptoms, such as fever $> 38.5^{\circ}\text{C}$ (e.g., for febrile neutropenia, an ANC $< 1000/\text{mm}^3$ with single temp of 38.3°C [101°F] or a sustained temperature of $\geq 38^{\circ}\text{C}$ [100.4°F] for more than one hour)
- Grade ≥ 3 thrombocytopenia with medically concerning bleeding
- Any Grade ≥ 4 hematologic AE, except:
 - Isolated Grade 4 lymphopenia without clinical correlate
 - Any Grade 4 neutropenia of < 7 days' duration not associated with any clinical symptoms
- All events of ALT $\geq 3 \times$ upper limit of normal (ULN) and bilirubin $\geq 2 \times$ ULN ($> 35\%$ direct bilirubin) or ALT $> 3 \times$ ULN and international normalized ratio (INR) > 1.5 , if INR measured, may indicate potential severe liver injury (possible Hy's Law), will require prompt permanent discontinuation from the study, and will be reported as an SAE (excluding studies of hepatic impairment or cirrhosis):
 - Without initial findings of cholestasis (elevated serum ALP).
 - In the absence of other reasons than drug toxicity to explain the laboratory constellation (e.g., viral hepatitis A, B, C or co-medication).
 - In the absence of other reasons than drug toxicity to explain the laboratory constellation.
- Any AE leading to the inability to deliver at least 80% of the planned total dose for the DLT period, except in situations other than toxicity, e.g. participant noncompliance or logistical issues with study intervention delivery.
- Death not clearly attributed to underlying disease or alternative cause.
- Additionally, the SMC may identify as a DLT:
 - A TEAE (inside or outside of the DLT period) that in the opinion of the SMC is of potential clinical significance such that further dose escalation would expose participants to unacceptable risk

The SMC must confirm any DLT.

If any change is made to the grade or causality of an AE during the study that may alter its DLT status, the Sponsor must be informed immediately as this may affect dose escalation decisions.

Additionally, participants excluded from the DLT analysis set may be replaced; the decision will be made by the SMC.

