1.3 Schedule of Activities

The Schedule of Activities for Part 1A (M4076 Monotherapy Dose Escalation) daily dosing schedule of this study is provided in [Table 1](#). Additional assessments may be performed at unscheduled time points if clinically indicated at the Investigator's discretion. To facilitate timely administration of study intervention, safety laboratory samples may be obtained up to 3 days before dosing. If laboratory samples are drawn before the day of dosing, they should be recorded in the case report forms (CRF) corresponding to the day of planned M4076 administration. The Part 1A pharmacokinetic (PK), electrocardiogram (ECG) and pharmacodynamic (Pd) biomarker assessments schedule is detailed in [Table 3](#).

The Schedule of Activities for Part 1B (preliminary Food Effect Assessment) is provided in [Table 2](#). The Part 1B PK, ECG, and Pd biomarker assessments schedule is detailed in [Table 4](#).

For Part 1A, potential variations in study intervention schedules and schedule of activities due to alternative dosing schedules are found [Appendix 7](#). Please see Sections [4.1.1](#) and [4.1.2](#), and [Appendix 12](#) for details on model for Bayesian dose escalation.

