1.3.1 Part 1A – M4076 Monotherapy Dose Escalation (Daily Dosing)

The schedule of events for Part 1A are provided in [Table 1](#).

The Part 1A fasting window is defined as: 2 hours predose to 1-hour postdose in general, and ~~C~~ hours predose to 4 hours postdose on days where PK-time matched triplicate ECGs are collected.

~~C~~
I

Table 1 Schedule of Activities: M4076 Monotherapy Dose Escalation (Daily Dosing), Part 1A

Assessments and Procedures	Screen (D -28 to -1)	DLT Period (21 days)					Subsequent 3-week Periods (21 days)			End of Study Intervention Visit	Safety Follow up/ Discontinuation Visit	Notes
Day		1	2	8	9	15	1	8	15	Within 7 days after last dose	30 days after last dose	
Visit Window (days)		-1								+7	+/- 7	Day 1 assessments that could be completed on Day -1 are limited to physical examination, height/weight, and ECOG performance status.
Study Site Visits	X	X	X	X	X	X	X	X	X	X	X	Starting Cycle 4, visits at Day 8 and Day 15 are optional
Written informed consent	X											
Inclusion / Exclusion Criteria	X											
Medical History (includes substance usage); Demography	X											Substances: tobacco use only.
Hepatitis B and C tests	X											To rule out active infection, performed at the Investigator's discretion. See Appendix 6 for details.
Optional HIV Screening	X											HIV testing is optional at the Investigator's discretion unless required locally.

Assessments and Procedures	Screen (D -28 to -1)	DLT Period (21 days)					Subsequent 3-week Periods (21 days)			End of Study Intervention Visit	Safety Follow up/ Discontinuation Visit	Notes
Day		1	2	8	9	15	1	8	15	Within 7 days after last dose	30 days after last dose	
Visit Window (days)		-1								+7	+/- 7	Day 1 assessments that could be completed on Day -1 are limited to physical examination, height/weight, and ECOG performance status.
Serum Pregnancy Test (WOCBP only)	X									X		See Section 8.3.5.
Urine Pregnancy Test (WOCBP only)		X				X						Urine β -hCG results must be available prior to M4076 dosing.
Physical Examination	X	X		X	X	X				X	X	See Section 8.2.1.
Height and Weight	X	X				X				X	X	Collect height at Screening only.
Imaging Disease Assessment (CT/MRI)	X	X (at the end of every 6 weeks for the first 24 weeks, then every 12 weeks)								X		Tumor assessment according to RECIST 1.1 until disease progression, end of study, or death, whichever is earlier. See Section 8.1 for details of imaging.

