Vital signs	X	X	X	X	X					X	X	In the first 6 weeks on study treatment, vital signs are measured as follows: 
 • Predose (within approximately 30 to 60 minutes prior) • 4 hours (\pm1 hour) postdose on Day 1 and Day 8. After 6 weeks, vital signs to be measured predose.
Standard 12-lead ECG	X					X post dosing				X	X	
Triplicate digital ECG		X	X	X								See Table 3 for triplicate ECG details.

Assessments and Procedures	Screen (D -28 to -1)	DLT Period (21 days)					Subsequent 3-week Periods (21 days)			End of Study Intervention Visit	Safety Follow up/ Discontinuation Visit	Notes
Day		1	2	8	9	15	1	8	15	Within 7 days after last dose	30 days after last dose	
Visit Window (days)	-1									+7	+/- 7	Day 1 assessments that could be completed on Day -1 are limited to physical examination, height/weight, and ECOG performance status.
ECOG performance status	X	X					X			X	X	See Appendix 10 .
AE, AESI and SAE assessment	Continuous										From time of signing the ICF through the Safety Follow-up Visit, and until completion of the study. SAEs and AESIs should be followed until resolution, stabilization, the event is otherwise explained, or the participant is lost to follow-up (see Section 8.3.3).	
Concomitant medications and procedures (including collection of subsequent anticancer therapy)												
Serum Chemistry	X	X	X	X		X	X	X	X	X	X	For Visit 1/D1, sample can be collected up to 72 hours prior to dosing. D8 and D15 assessments are optional after Week 9. See Appendix 6 for details.
Hematology and Coagulation (PT, aPTT, INR)	X	X	X	X		X	X	X	X	X	X	For Visit 1/D1, sample can be collected up to 72 hours prior to dosing. D8 and D15 assessments are optional after Week 9. See Appendix 6 for details.
Urinalysis	X	X				X	X			X		See Appendix 6 for details.

Assessments and Procedures	Screen (D -28 to -1)	DLT Period (21 days)					Subsequent 3-week Periods (21 days)			End of Study Intervention Visit	Safety Follow up/ Discontinuation Visit	Notes
Day		1	2	8	9	15	1	8	15	Within 7 days after last dose	30 days after last dose	
Visit Window (days)		-1								+7	+/- 7	Day 1 assessments that could be completed on Day -1 are limited to physical examination, height/weight, and ECOG performance status.

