9.4.2 Safety Analyses

The DLT analysis will be performed on the DLT Analysis population. All other safety analyses will be performed on the Safety Analysis population. See [Table 17](#).

Table 17 Safety Analyses

Endpoint	Statistical Analysis Methods
Part 1A	
Primary	
DLT	
AEs classified as DLTs as assessed by SMC will be evaluated.
 
Bayesian dose toxicity analysis.
 
At primary analysis for Part 1A, the number and proportion of participants experiencing DLTs will be reported by dose level, based on observations during the first study intervention evaluation (21 days). Posterior probabilities (2.5%, 25%, 50%, 75%, and 97.5% quantiles) for DLT rates at selected doses will be estimated from the Bayesian dose toxicity model.
 
Sensitivity analysis using frequentist modeling (without prior).
 
Regarding intercurrent events: These are considered in the definition of DLTs and DLT analysis set.

Secondary	
AE	
AEs will be coded according to the latest available version of MedDRA. Severity of AEs will be graded using the NCI-CTCAE (Version 5.0). Missing classifications concerning study intervention relationships will be considered related to the study intervention. TEAEs are defined as AEs emerging or worsening after start of study intervention until 30 days after the end of study intervention period.
 
Following TEAEs will be presented in summaries by incidence and type according to MedDRA System Organ Classes and Preferred Terms:
 
 • TEAEs. • SAEs. • TEAEs related to study interventions. • NCI-CTCAE Grade 3 or higher TEAEs. • NCI-CTCAE Grade 3 or higher related TEAEs. • TEAEs leading to interruptions, dose modifications of study interventions. • TEAEs leading to permanent discontinuation of study interventions. • TEAEs leading to death.

Death	Counts and percentages.
Changes in laboratory measurements	Summary statistics and boxplots. Laboratory results will also be classified by Grade according to NCI-CTCAE. Worst on-treatment grades as well as shifts to worst on treatment grades will be summarized. Measurements without NCI-CTCAE grading will be summarized by above, within and below normal limits.

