9.4.4 Sequence of Analyses

SMC for Part 1A: The SMC will review available data during study conduct. The cut-off for dose escalation assessments by the SMC will usually be triggered by the completion of the DLT period (or dropout) of the last participant in the respective dose escalation cohort of usually 3 participants. When enrolment of last participant in a dosing cohort is delayed, the SMC may decide (based on available data) upon enrolment and dose for the next dosing cohort before all participants in a cohort have completed 21 days. The Bayesian model will then be updated with the available data, and the data from the participant not having completed the DLT period at time of SMC will be considered in the next SMC. In these cases, cut-off can be earlier (after DLT period of the first 2 subjects is finished or they experienced a DLT).

SMC for Part 1B: The cut-off of the SMC will be triggered when the 6th participant has been treated for 28 days (or has dropped out). The SMC will be supported by the results of the Bayesian model used in Part 1A.

Primary analysis for dose escalation

The cut-off for an exploratory analysis of the safety, available PK, available Pd and preliminary antitumor activity data from Part 1A will be triggered when all participants have reached either the first on-treatment tumor assessment, or experienced death or premature withdrawal for any reason, whichever comes first.

Final Analysis for Part 1A and 1B

Follow-up analyses to report further efficacy, safety, and PK data if applicable for Part 1A and all analyses for Part 1B will be performed once the End of Study has been reached.

Additional Analyses

Further analyses may be performed, e.g. for publication purposes or decision-making purposes.

More details will be described in the iAP.

10

References

Curtin NJ. DNA repair dysregulation from cancer driver to therapeutic target. *Nat Rev Cancer*. 2012;12:801-17.

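### Part 1A requires no safety laboratory sample on Days 16-21 of the DLT period, so detection and counting of late asymptomatic laboratory DLTs is not guaranteed

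*Protocol*

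**What the plan says.** Protocol 6.6.2 requires a DLT to be an adverse event that occurs within the DLT observation period, which for Part 1A "starts on the first day of study intervention (Day 1) and has a duration of 21 days". Two other places repeat the window. The first criterion for the DLT analysis set (Protocol 9.3, SAP 8.1) asks for a DLT in the DLT period, and Table 17 in Protocol 9.4.2 limits the reported DLT proportion to observations over 21 days.

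Table 1 (Protocol 1.3.1) has visits in the DLT period on Days 1, 2, 8, 9 and 15. The serum chemistry row and the hematology and coagulation row are marked on Days 1, 2, 8 and 15, but not on Day 9. The next mark is Day 1 of the following three-week period.

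Four other provisions bear on the point:

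- Protocol 1.3 says that "safety laboratory samples may be obtained up to 3 days before dosing", and that such a sample goes on the CRF page "corresponding to the day of planned M4076 administration". The Table 1 laboratory notes give a 72-hour allowance only for Visit 1/Day 1. Section 1.3 also permits unscheduled assessments when clinically indicated.
- Protocol 6.6.2 lets the SMC name as a DLT a treatment-emergent event outside the period, if in its opinion the event would make further escalation an unacceptable risk.
- Protocol 9.4.4 says the SMC cut-off is usually "triggered by the completion of the DLT period (or dropout) of the last participant" in the cohort.
- SAP 15.1 says the SMC minutes are updated if a DLT appears after the period, and it fits the final models to DLTs as decided by the SMC.

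**The concern.** The window and the laboratory schedule are out of step by one day. The sample that would close out the DLT period is scheduled for the day after it ends. Protocol 1.3 implies that this sample is taken before dosing, so it reflects exposure to DLT-period doses only.

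The affected participant does not drop out of the analysis. Someone who took at least 80% of the planned dose and completed the period enters the DLT set under its second criterion. If the Day 22 finding is not counted, that person enters the model as evaluable without a DLT. The error therefore runs in one direction: a lower recorded DLT rate and a recommendation tilted toward escalation.

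DLT occurrence is a primary endpoint and the only outcome that updates the dose-toxicity model (Protocol 9.4.2.1). Laboratory-detected DLTs are plausible for this drug. Section 6.6.2 lists Grade 4 hematologic events and a combined ALT, bilirubin and INR criterion, and cytopenia is the protocol's only adverse event of special interest (8.3.6).

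**Working it through.** **Step 1: the calendar.** The last DLT day is 1 + 21 - 1 = Day 21, which reproduces the stated 21 days. Day 1 of the next period is Day 22, which agrees with the Day 22 entries in Tables 1 and 3.

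**Step 2: required laboratory days (Table 1).** These are Days 1, 2, 8, 15, then 22, 29 and 36. The last inside the window is Day 15. The days after it and inside the window are 16-21, which is 6 of 21 (6/21 = 28.6%).

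**Step 3: the early-draw allowance (Protocol 1.3).** If the 3-day allowance applies to the Day 22 sample:

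| Day drawn | Onset days in the gap that it can detect | Sample inside the DLT period? |
|---|---|---|
| 19 | 16-19 | Yes |
| 20 | 16-20 | Yes |
| 21 | 16-21 | Yes |
| 22 | 16-21 | No |

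Only a Day 21 draw covers the whole gap from inside the window. The early draw is optional, and a sample from any of these days is recorded under the planned dosing day.

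**Step 4: effect on the recorded rate.** Let s be the share of DLTs that only a laboratory test would reveal. The documents do not give s, so a range is shown. Further assumptions:

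- DLT onset is uniform over Days 1-21.
- An abnormality persists until the next sample, so those arising by Day 15 are all found.
- No laboratory-only event from Days 16-21 is rescued by an early draw, an unscheduled test, onset dating or an SMC decision.

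The true rate is set at 30%, the protocol's target for the MTD.

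Recorded rate = 0.30 x (1 - s x 6/21). P(0 DLT in 3) = (1 - recorded rate)^3.

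| s | Recorded rate | P(0 in 3) |
|---|---|---|
| 0 (true rate) | 30.0% | 0.700^3 = 34% |
| 10% | 29.1% | 0.709^3 = 36% |
| 25% | 27.9% | 0.721^3 = 38% |
| 50% | 25.7% | 0.743^3 = 41% |
| 100% | 21.4% | 0.786^3 = 49% |

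For 6 participants, P(0 DLT) is 0.700^6 = 12% at the true rate and 0.786^6 = 24% at s = 100%.

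**The case against.** A reader might infer that laboratory toxicity arising on Days 16-21 is found too late to count, or that no laboratory check on those days can yield a DLT. The documents support neither reading:

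- Section 6.6.2 turns on when the event occurs, and nowhere is onset equated with the date of detection. The AE start date is a separate item in the SAP 15.1 listing, and SAP 15.4 plots key laboratory values by actual day.
- The Day 22 sample may be drawn on Days 19-21, and unscheduled tests are allowed.
- The SMC may name a DLT outside the period. SAP 15.1 updates the minutes for late DLTs and carries SMC-decided DLTs into the final model without a 21-day filter.
- Section 6.6.2 excepts many asymptomatic findings: single laboratory values without clinical correlate that resolve within 7 days, asymptomatic Grade 3 lipase or amylase elevation, isolated Grade 4 lymphopenia, and asymptomatic Grade 4 neutropenia of under 7 days. The risks that the protocol added from this study's clinical data, rash and hypersensitivity, show themselves by symptoms.
- The cut-off in 9.4.4 is the usual one, not a fixed one. Participants dosed earlier in a cohort would normally have Day 22 results by then. Minimum data requirements sit in the SMC charter, which is not among the documents, so it cannot be said that the SMC will meet without those results.

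These points defeat the absolute reading and make the 30%-to-21% figure a ceiling. They do not close the gap. The early draw is optional, its scope is unclear between Section 1.3 and Table 1, and its CRF entry can obscure an in-period date. Unscheduled tests need a clinical indication, which an asymptomatic event may not give. The SMC clause is discretionary and limited to events that bear on further escalation; it does not say that an event meeting an ordinary DLT criterion counts when found on Day 22. Neither document says how to date an abnormality first seen on that day.

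**Conclusion.** The point holds in a limited form. Under daily dosing in Part 1A, no safety laboratory sample is required after Day 15 and within the DLT period. Detection and counting of asymptomatic laboratory DLTs arising on Days 16-21 is therefore not guaranteed. For the last participant in a cohort, the Day 22 result may also fall after the usual SMC cut-off. Symptomatic DLTs are unaffected.

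The size rests on the unknown share s and on no event being rescued. If a quarter of DLTs are laboratory-only, the loss is about 2 percentage points from a true 30%; at a half it is about 4. The loss of nearly 9 points needs every DLT to be laboratory-only and none of the late ones counted, so it should not be read as an expected bias. Onset concentrated late in the period would raise these figures, and any rescue would lower them.

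The severity is moderate. A primary endpoint can be misclassified in the direction of escalation with cohorts of 3, and a sample already scheduled would prevent most of it.

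**What to change.** - In Protocol 6.6.2 and 9.3 and in SAP 8.1, state that DLT ascertainment includes the already scheduled Day 22 pre-dose safety laboratory results, so that an abnormality meeting a DLT criterion on that sample counts. Align the 21-day wording in Table 17.
- Classify laboratory events by actual sample date, not by CRF visit.
- Reconcile the general early-draw allowance in Section 1.3 with the Visit 1/Day 1 note in Table 1.
- In Protocol 9.4.4, set the usual SMC cut-off after the last participant's Day 22 pre-dose results, and mirror this in the SMC charter.

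No visit or sample is added. The cost is amended wording, about one day's wait for the SMC, and possibly a slightly higher observed DLT rate.
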